#### 5.4 Covariates

All covariates are defined based on available information within the 12-month period prior to and including the date of the first long-acting insulin prescription. It is important that this time is constant irrespective of the availability of additional data.

The minimum set of covariates includes age, gender, cohort entry date, co-morbidities (e.g., COPD as proxy for smoking), co-medication (including but not limited to other antidiabetic medications), health care system use (number of in- and outpatient encounters, days hospitalized), and screening behavior (especially cancer screening, see table). If available, smoking status, family history of cancer (overall and specific cancers, if available), body mass index, and duration of diabetes are also covariates of interest.

Potential confounders for specific types of cancers include use of hormone therapy and use of oral contraceptives.

Covariates by category are as follows:

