# 5.5 Baseline and follow-up (time at risk)

Baseline is defined as the 12-month time period up to and including the date of first prescription of glargine or NPH for new users; all covariates will be assessed based on data from this 12-month period. The start of follow-up for Ochsner and Partners HealthCare System patients will be the date of the first prescription. The start of follow-up for new users in the MedAssurant database will be defined for each cohort member as the date of the second prescription for glargine or the glargine comparator insulin. Note that the first and second prescriptions can be for different insulins as long as both insulins reside within the same group (i.e. glargine or NPH,).

The use of the second prescription allows us to remove patients who filled a prescription but were minimally or never exposed to the insulin products of interest. The potential for this kind of exposure misclassification is much smaller given the dispensing of a second prescription. The use of the second prescription as the start of follow-up results in the potential for changes in prescribed type of insulin (see above), covariates, and exclusion criteria. We will ignore changes in covariates because such changes may already be affected by the first prescription. Patients developing cancer between the first and second prescription will be flagged, enumerated, and excluded from the primary analysis.

Follow-up will generally end at: (1) diagnosis of any cancer (except non-melanoma skin cancer) for both overall cancer and specific subgroups, (2) death, (3) a gap of greater than 6 months in either membership or prescription benefits (if membership is not well defined, if no diagnostic code OR no prescription for

more than 6 months during follow-up; a final determination will be made following a review of the data), or (4) the end of the study (date to be determined with individual sites); whichever comes first. In addition, for the analyses on breast, colon, and prostate cancer risk, patient follow-up will be censored when the target organ is removed for a non-cancer related reason.

- For the breast cancer analysis, complete bilateral mastectomy;
- For the colon cancer analysis, removal of colon;
- For the prostate cancer analysis, complete prostatectomy, when done for reasons not related to prostate cancer.

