Stopping, switching, augmenting: Because we are interested in potential harm, the primary analysis will be as treated. Therefore, in the primary analysis that compares new users of glargine with new users of NPH, patients stopping the corresponding drug (glargine or NPH), switching to another long-acting insulin (including detemir), or augmenting with another long-acting insulin will be censored at that point in time. Patients who take a premixed analog insulin during follow-up will be treated in a similar manner (i.e. censored at that point in time). Patients who do not refill their insulin prescription within a period equal to the total days of supply (plus a 6 months grace period) will be treated as if they stopped taking insulin at the end of that period (i.e. they will be censored at the last prescription date plus [the days of supply plus 6 months]). If no information on days of supply is available, an informed guess will be made based on the specific study site (i.e., median days of supply).

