# 5.6 Statistical Analysis Methods

# 5.6.1. New User Analysis

The new user analysis (Ray 2003) will be based on a defined period of no insulin use prior to the first eligible prescription. To do so, all patients with a prescription of any insulin during the 19 months prior to the first eligible prescription will be excluded. The only exception will be for patients with only one prescription for a short-acting insulin. To allow for treatment titration and therefore better account for early switching, treatment augmentation, and non-chronic use, follow-up will not start at drug initiation but rather at the second prescription after initiation as outlined above. In cases where only one record is necessary to define the cohort (i.e. Ochsner and Partners HealthCare), follow-up will begin at drug initiation.

For the primary analysis, follow-up will start at the time-point defined above for all cohorts. To allow for time-varying hazard ratios (e.g., varying induction periods), we will stratify the follow-up into 0-<6 months, 6-<9 months, 9-<12 months, 12-<24 months, and 24+ months.

Augmentation with short-acting insulin during follow-up will be ignored for the primary analysis but will be described. To do so, time of a first prescription of a short-acting insulin will be ascertained as a separate variable (as well as specific formulation and dose).

The effect of cumulative insulin dose will be addressed by calculating the cumulative insulin dose as of every new prescription and categorizing patients into mutually exclusive categories of cumulative dose (e.g., >0-<=10kU, >10-<=20kU, >20-<=40kU, >40kU). We will categorize cumulative dose based on the long-acting insulin exclusively as well as on long-acting plus short-acting insulin combined. Time at risk for malignancies will start once a patient reaches the corresponding cumulative dose and end once a patient reaches the next cumulative dose level.

In the as treated new user design, follow-up time equals time on treatment since initiation and thus is an indicator of cumulative dose (while being less affected by intermediates). We will therefore also stratify follow-up time (e.g., 0-6, 6-12, 12-24, 24+ months; see above).

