We will implement the propensity score by stratification (deciles) and inverse probability of treatment weighting (IPTW). Balance of important covariates will be assessed within deciles of the propensity score and in the weighted pseudo population. Any imbalance will be interpreted according to the potential of the imbalanced covariate to affect the risk for the outcome. Given balanced covariates and under the assumption of no unmeasured confounding, incidence rates and survival curves are adjusted or unconfounded and thus can be directly compared. Time trends in absolute and relative hazards will be assessed by stratifying on months of follow-up time (0-6, 6-12, 12-24, 24+). The main measure of association will be the hazard ratio estimated using a Cox proportional hazards model controlling for age and sex as well as any covariates remaining imbalanced after implementation of the propensity score.

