Appendix C
Table of Planned Secondary and Sensitivity Analyses

Rank	Primary Analysis	Secondary Analyses	Rationale
Secondary Analyses			
1	Incident users	Perform analysis of prevalent users	Increase number of patients in study; confirm that results are similar to the new user analysis results.
2	All patients with diabetes	Exclude patients less than 40 years old or who do not have at least two prescriptions for oral hypoglycemic medications not more than 6 months apart during the baseline period.	Patients who meet these criteria will nearly all be Type II diabetics.
Sensitivity analyses			
1	Entire available follow-up	Stratify follow-up into 0-6 months, 6- 12 months, 12-24 months and >24 months after baseline	Allow for changing hazard ratios with time after initiation
2	Baseline (date of second prescription)	Begin follow-up 6 months, 9 months, 12 months and 24 months after baseline	Allow for varying induction periods  Note that this analysis is very similar but not exactly the same as the above

Rank	Primary Analysis	Secondary Analyses	Rationale
3	Censor immediately at stopping (plus grace period), switching, augmenting	Censor follow-up time 3 months, 6 months, 12 months and 24 months after a censoring event* (stopping, switching or augmenting). Both events and person-time during these periods after stopping, switching, augmenting will be counted towards the treatment preceding these events.  * Note that this applies only to censoring due to stopping, switching, augmenting; all other censoring (e.g., eligibility, calendar year) remain unchanged	Allow for varying latency periods for treatment effects
4	As treated	Do not censor follow-up time after a censoring event* (ITT analysis)  * Note that this applies only to censoring due to stopping, switching, augmenting; all other censoring (e.g., eligibility, calendar year) remain unchanged	Minimize the potential for selection bias
5	Exclude only non-overlapping propensity score regions	Exclude 1%, 2.5%. and 5% of those in the tails of the overlapping propensity score distribution, i.e., asymmetric trimming of those treated contrary to prediction	Most likely to have unmeasured confounders

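### As-treated hazard ratios by time band, and the delayed-start analyses, also need censoring at stopping, switching or augmenting to be non-informative; the plan neither states nor checks this

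*Protocol*

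**What the plan says.** All references are to the Protocol.

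- **Covariates (5.4):** "All covariates are defined based on available information within the 12-month period prior to and including the date of the first long-acting insulin prescription". On changes between the first and second prescription, 5.5 says: "We will ignore changes in covariates because such changes may already be affected by the first prescription".
- **Adjustment (5.6.1):** "We will implement the propensity score by stratification (deciles) and inverse probability of treatment weighting (IPTW"). Balance is to be assessed within deciles and in the weighted population. The Cox model then adjusts for age, sex and any covariate still imbalanced. No step is tied to a point in follow-up.
- **Inference from balance (5.6.1):** given balance and no unmeasured confounding, "incidence rates and survival curves are adjusted or unconfounded and thus can be directly compared". The next sentence plans the time trends: "Time trends in absolute and relative hazards will be assessed by stratifying on months of follow-up time (0-6, 6-12, 12-24, 24" months and over).
- **Censoring (5.5):** the primary analysis is as treated. Patients who stop or switch leave follow-up, and those "augmenting with another long-acting insulin will be censored at that point in time".
- **Delayed starts (Appendix C, sensitivity analysis 2):** "Begin follow-up 6 months, 9 months, 12 months and 24 months after baseline".
- **Related analyses (5.6.2, Appendix C):** censoring lagged by 3, 6, 12 and 24 months, and an ITT analysis whose stated purpose is to limit selection bias. Neither is linked to the time bands.

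Section 5.6.1 also gives a second, finer set of bands: "we will stratify the follow-up into 0-<6 months, 6-<9 months, 9-<12 months, 12-<24 months, and 24+ months".

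**The concern.** Balance at the start of follow-up does not carry forward by itself when follow-up ends at treatment change. Everyone in a later as-treated band, or in an analysis that starts at 6 to 24 months, has persisted with the initial insulin. If a cancer risk factor drives patients off one insulin more than off the other, the two sets of persisters differ on that factor even though the initiators did not. Treatment weights built at entry describe who started which drug, not who stayed on it.

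So the comparability statement in 5.6.1 lists two conditions where the as-treated analysis needs a third: censoring that is non-informative given the adjusted covariates. Section 5 itself uses differential dropout and the resulting survivor cohort as an argument against prevalent-user designs. A follow-up that starts 12 or 24 months in has the same structure.

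The stake is interpretation. Section 5.6.1 gives varying induction periods as a reason for the bands and treats time on treatment as a marker of cumulative dose. A drift produced by selective persistence could be taken for an induction or dose effect, or could hide one.

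**Working it through.** The protocol gives no discontinuation data and no banded figure to reproduce, so this is an illustration of size.

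**From the protocol:** bands 0-6, 6-12, 12-24 and 24+ months (5.6.1); median follow-up about 2 years in each arm (section 6).

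**Assumed:** true hazard ratio 1; a binary risk factor with prevalence p = 0.30, balanced at entry; cancer risk ratio RR = 2; exponential exit; follow-up cut at 5 years; the factor multiplies the treatment-related exit hazard by k in one arm only; c is the exit hazard unrelated to treatment.

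**Formulas**

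1. Base exit hazard h in each arm, from the 2-year median: p·exp(−2(c+kh)) + (1−p)·exp(−2(c+h)) = 0.5.
2. Person-time in band (a, b) at hazard λ: T(λ) = [exp(−λa) − exp(−λb)]/λ.
3. Prevalence of the factor in the band: P = p·T(c+kh) / [p·T(c+kh) + (1−p)·T(c+h)].
4. Apparent ratio, glargine to NPH: [1 + P_G(RR−1)] / [1 + P_N(RR−1)].

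**Solved hazards per year.** With c = 0, glargine (k = 1) has h = ln2/2 = 0.3466; NPH has 0.3054 (k = 1.5) or 0.2781 (k = 2). If half of exit is unrelated to treatment, c = 0.1733; glargine h = 0.1733, NPH h = 0.1517 or 0.1362.

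**Apparent ratios when the true ratio is 1**

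| Exit effect of the factor | 0-6 | 6-12 | 12-24 | 24+ |
|---|---|---|---|---|
| 1.5-fold, NPH only | 1.006 | 1.018 | 1.036 | 1.076 |
| 2-fold, NPH only | 1.011 | 1.033 | 1.064 | 1.131 |
| 1.5-fold, NPH only, half of exit unrelated | 1.003 | 1.009 | 1.018 | 1.039 |
| 2-fold, NPH only, half of exit unrelated | 1.005 | 1.016 | 1.032 | 1.069 |
| 2-fold, glargine only | 0.989 | 0.968 | 0.940 | 0.884 |
| 2-fold, both arms, same base | 1.00 | 1.00 | 1.00 | 1.00 |

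The last column for NPH-only effects can be checked by hand. Glargine prevalence stays at 0.30, while NPH prevalence falls to 0.208, 0.150, 0.251 and 0.216 in the four rows. The ratios are 1.30/1.208, 1.30/1.150, 1.30/1.251 and 1.30/1.216.

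**Delayed starts.** A start at 24 months uses the same person-time as the last band, so the ratio is the same. With a set to 0.5, 0.75 or 1 year, b = 5 and c = 0, starts at 6, 9 and 12 months give 1.05, 1.06 and 1.06 (k = 1.5) or 1.09, 1.10 and 1.10 (k = 2).

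**Range over RR.** For RR = 1.5 and 3, the 2-fold NPH case gives 1.07 and 1.23 beyond 24 months, and the mirror case 0.94 and 0.81 (c = 0).

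**Do the remedies work?** A simulation of 4 million subjects (RR = 2, 2-fold in NPH only) gave as-treated ratios of 1.02, 1.04, 1.04 and 1.11. Censoring weights given arm and the factor gave 1.00, 1.01, 0.98 and 0.98, as did adjusting for the factor within each band. ITT gave 1.00 in all four. Simulation error is roughly 0.01 to 0.02.

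**The case against.** **The effect is conditional.** A reader might infer that a trend is built into the design. It is not. Drift needs exit that depends on cancer risk and does so differently by arm. It is absent if exit hazards are the same in both arms, or differ by arm but not by risk. (A 2-fold effect in both arms on unequal base rates, 0.20 and 0.35 per year, does leave some drift: 1.09 beyond 24 months at RR = 3. Those rates would not give equal medians.) The equal medians in section 6 neither show nor exclude the problem, since the table holds them equal.

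**Larger figures are not supported.** Leaving the NPH base hazard at ln2/2 and adding the exit effect on top gives 1.09 and 1.15 beyond 24 months, but the NPH median then falls to 1.76 or 1.60 years, against the stated 2. Nor can the result be said to breach the plan's own tolerance: the 10% cut point in 5.6.1 was set for confounding by BMI, not for selection within time windows.

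**Protections exist.** Age and sex are in the Cox model. Decile stratification conditions partly on measured factors throughout follow-up. Lagged censoring keeps leavers at risk for a time, and ITT removes this censoring. This stands for the overall hazard ratio. For the bands it is incomplete: lags and ITT are not specified by band. The final score keeps only cancer risk factors among the 10 covariates most associated with channeling, so a factor balanced at entry may be in neither score nor model.

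**Late bands are imprecise.** The section 6 minimum ratios imply D = (1.96+0.84)²/[0.8267×0.1733×(ln RR)²]: about 1,649 events for any cancer, 303 breast, 262 prostate and 187 colon. With about 39% of person-time beyond 24 months, (0.5−0.177)/(1−0.177), the 95% limits there, exp(1.96/√(0.39·D·0.8267·0.1733)), are about ×/÷1.23, 1.61, 1.67 and 1.83. The drift is smaller than any of these in the main cases, but it is systematic, and combining sites does not average it away if they share it.

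**The primary result is not overturned.** Appendix C makes the entire follow-up primary; bands and delayed starts are sensitivity analyses. Window-specific tables could also sit in a separate analysis plan that is not at hand. The incomplete condition, however, is stated in the protocol itself.

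**Conclusion.** The point holds in a limited form. The comparability statement in 5.6.1 omits a condition that the as-treated censoring in 5.5 makes necessary, and no planned step secures that condition for the time bands or the delayed starts. The likely distortion is modest: close to nothing in the first six months, and about 1.08 to 1.13 beyond 24 months under the assumed inputs, or 1.04 to 1.07 if half of exit is unrelated to treatment. With the effect in the glargine arm the ratios fall below 1 by a similar proportion. Whether it occurs at all, and in which direction, cannot be told from the protocol. It bears on how a trend over time on drug is read, not on whether the overall analysis is valid. It merits a change because the check is cheap and the late windows are those used to judge induction.

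**What to change.** 1. In 5.6.1, add to the comparability statement that as-treated censoring must be non-informative given the adjusted covariates.
2. Tabulate baseline covariate balance, weighted and within deciles, among patients still at risk at 6, 12 and 24 months, and at 9 months for that delayed start. Settle which of the two sets of bands in 5.6.1 applies.
3. Apply the existing rule on covariates that remain imbalanced within each window and each delayed-start analysis. Alternatively, multiply the treatment weights by inverse-probability-of-censoring weights built from baseline covariates. Re-estimating the propensity score at each delayed start is optional.
4. Repeat the banded hazard ratios under ITT and report them beside the as-treated ones.

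All of this uses data already held. The cost is some programming and somewhat wider intervals in the late windows. It does not correct for factors that claims data lack, such as BMI and smoking, and the report should say so.

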# 5.6.2 Prevalent User Analysis and Other Subgroup and Sensitivity Analyses

In addition to the new user analysis described above, each group (UNC-CH and MedAssurant) will conduct an analysis of prevalent users using the same dataset that was used for the new user analysis, except patients with prescriptions for insulins prior to the first eligible prescription will not be excluded. Additional details about this analysis can be found in *Cohort study of insulin glargine and cancer risk among patients with diabetes mellitus (Kaiser Permanente, Northern and Southern California Regions)*. Results from the prevalent user analysis, including site-specific results and also combining across sites through meta-analysis, will also be reported. If the combined hazard ratios of glargine versus NPH differ substantially for the new user and prevalent user analyses for any of the four endpoints, then exploratory analyses will be carried out to explain the discrepancies.

For the new user analysis, sensitivity analyses will allow for varying latency periods of drug effects. To do so we will have additional variables censoring follow-up time 3 months, 6 months, 12 months, and 24 months after exposure defined censoring events (stopping, switching or augmenting) as described in Section 5.5. In these analyses, both events and person-time during these periods after stopping, switching, or augmenting will be counted towards the treatment preceeding these events. In addition, ITT analyses are also planned where we do not censor for augmentation, switching or stopping (i.e., counting all events until death or administrative censoring).

A complete list of planned subgroup and sensitivity analyses is included in Appendix C.

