#### **Cohort Eligibility**

[figure not shown]
If  $W_1 > WP$  then patient's period of drug use is eligible for the new user cohort.

If  $W_i$  > WP and i>1 then patient's period of drug use is eligible for new user cohort **IFF** the analysis allows for previous users to become new users.

If i=1 then patient's period of drug use is eligible for the prevalent user cohort regardless of the value of  $W_1$ 

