#### **Algorithm**

- 1. Set (Start of Washout Period) = (Start of Continuous Enrollment).
- 2. Set (Index Date) = (1st RX Fill Date following Start of Washout Period). Let *W* = (Index Date) (Start of Washout Period). Flag the period of drug use for cohort eligibility based on the following criteria:
  - a. If this is the patient's first RX of record, then flag as the index date for the prevalent user cohort.
  - b. If this is the patient's first RX of record and W > (Washout Period), then flag as the index date for the primary new user cohort.
  - c. If W > (Washout Period), then flag as the index date for the secondary new user cohort.
- 3. Set (Last Day Covered) = (Index Date) + (Days Supply).
- 4. Let G = (RX Fill Date) (Previous Last Day Covered). Sequentially cycle through the subsequent prescription claims for the patient, applying the appropriate step below, until (Discontinuation Date) is set:
  - a. If G > (Grace Period) then set (Discontinuation Date) = max(Previous Last Day Covered, Date of RX Fill) + (Days Supply) + (Grace Period).
  - b. If G <= (Grace Period), set (Last Day Covered) = max(Previous Last Day Covered, Date of RX Fill) + (Days Supply). If (Last Day Covered) + (Grace Period) > (End of Continuous Enrollment) and the patient has no additional RX claims with (RX Fill Date) <= (End of Continuous Enrollment), then set (Discontinuation Date) = (End of Continuous Enrollment). Otherwise, repeat Step 3 for the next prescription.

- 5. Output a record containing Index Date, Discontinuation Date, and the cohort inclusion flags set in Step 2.
- 6. Set (Start of Washout Period) for the next period of use:
  - a. If the patient is continuously enrolled from (Discontinuation Date) to the next (RX Fill Date), set (Start of Washout Period) = (Discontinuation Date) + 1.
  - b. If the patient has a gap in enrollment between (Discontinuation Date) and the next (RX Fill Date), set (Start of Washout Period) = (Start of Next Period of Continuous Enrollment).
- 7. Repeat Steps 2-7 for the patient's remaining RX fills.

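### The prevalent-user analysis contains all primary new users, so comparing its hazard ratio with the new-user hazard ratio understates any difference between new users and patients with prior insulin

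*Protocol*

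**What the plan says.** Protocol section 5.6.2 has each analysis group run a prevalent-user analysis "using the same dataset that was used for the new user analysis". It states one departure from that dataset, on earlier insulin: "except patients with prescriptions for insulins prior to the first eligible prescription will not be excluded". No other change to the cohort is described there.

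Appendix A also builds an overlapping pair. Under Cohort Eligibility: "If i=1 then patient's period of drug use is eligible for the prevalent user cohort regardless of the value of" the washout length W. In Step 2 of the Algorithm, 2a reads "If this is the patient's first RX of record, then flag as the index date for the prevalent user cohort", while 2b requires "first RX of record and W > (Washout Period), then flag as the index date for the primary new user cohort". Section 5.1 (Subsequent Instances of New Use) limits the primary analysis to the first eligible prescription of glargine or NPH.

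The two results are then compared. Appendix C ranks the prevalent-user analysis first among the secondary analyses. Its stated reasons are to gain patients and to "confirm that results are similar to the new user analysis results". Section 5.6.2 calls for exploratory analyses if the pooled hazard ratios "differ substantially for the new user and prevalent user analyses for any of the four endpoints". It gives no threshold, test or allowance for shared patients.

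**The concern.** When one cohort contains the other, their estimates agree in part because they share patients and events. A reader of the final report would take similar hazard ratios as two designs supporting each other. Much of that agreement could be the new-user result counted twice.

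This matters here because the opening of section 5 justifies the new-user design by the biases of prevalent-user cohorts, chiefly survivor selection. The comparison in section 5.6.2 is where the protocol sets the two designs against each other. If patients with prior insulin gave a materially different hazard ratio, the planned comparison would show a smaller gap. The exploratory work might then not start. Neither section 5.6.2 nor Appendix C lists an estimate confined to patients with prior insulin, so the undiluted contrast would not be seen.

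**Working it through.** **Step 1: is the new-user cohort nested?** Section 5.6.2 lifts one exclusion and removes nobody. In Appendix A, condition 2b is condition 2a plus a washout requirement, applied to the same fill. Every 2b patient is therefore a 2a patient with the same index date. Repeat episodes (2c) do not break the nesting, because the primary analysis uses first episodes only. On either definition, all primary new users are in the prevalent-user cohort.

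**Step 2: how much of a difference remains visible?** Let w be the share of statistical information contributed by new users. To a first approximation,

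ln HR_all = w × ln HR_new + (1 − w) × ln HR_prior,

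so ln(HR_new / HR_all) = (1 − w) × ln(HR_new / HR_prior).

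Section 6 gives 47,227 new glargine and 9,899 new NPH users in MedAssurant, but no count of patients with prior insulin. So w is unknown, and 0.2 to 0.8 is an assumed range. The true ratios below are also assumed.

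| w | Visible ratio if true ratio is 1.50 | if 1.30 | if 1.20 |
|---|---|---|---|
| 0.2 | 1.38 | 1.23 | 1.16 |
| 0.3 | 1.33 | 1.20 | 1.14 |
| 0.5 | 1.22 | 1.14 | 1.095 |
| 0.7 | 1.13 | 1.08 | 1.06 |
| 0.8 | 1.08 | 1.05 | 1.04 |

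In the direction of survivor bias, with HR_new = 1.0 and an assumed HR_prior = 0.70, the prevalent-user analysis would report 0.70^(1 − w): 0.78, 0.84 and 0.90 at w = 0.3, 0.5 and 0.7.

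**Step 3: would the trigger be missed?** Section 5.6.2 gives no threshold. The only numeric change-in-estimate cut point in the protocol is ±10%, set in section 5.6.1 for confounding by BMI. Borrowing it as an assumption, a true ratio R goes unflagged when w > 1 − ln 1.10 / ln R. That is w above 0.48 for R = 1.2, 0.64 for R = 1.3 and 0.76 for R = 1.5. In the survivor-bias illustration, by contrast, 0.779, 0.837 and 0.899 are changes of 22%, 16% and 10.1% from 1.0, so all three would still be flagged.

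**Step 4: what does ignoring the overlap cost in a test?** The two log hazard ratios have correlation of about √w: 0.55, 0.71 and 0.84 at w = 0.3, 0.5 and 0.7. Section 6 gives minimum detectable ratios of 1.2 (any cancer) and 1.53 (breast) at 80% power and two-sided 5%, and the glargine share is 47,227 / 57,126 = 0.827. Schoenfeld's formula then implies about 1,649 and 303 new-user events. These are back-solved, not stated, and the breast figure assumes the same allocation among women. With V the new-user variance of the log hazard ratio and d = ln 1.5:

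- disjoint groups: z = d × √((1 − w)/V)
- nested estimates treated as independent: z = (1 − w) × d / √(V(1 + w))

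| Endpoint | w | Power, disjoint | Power, nested treated as independent |
|---|---|---|---|
| Any cancer | 0.5 | 0.99 | 0.72 |
| Any cancer | 0.7 | 0.93 | 0.30 |
| Breast | 0.5 | 0.47 | 0.19 |
| Breast | 0.7 | 0.31 | 0.09 |

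**Step 5: who is added to the new users?** Section 5.6.2 adds patients with recorded insulin before the first eligible prescription. Appendix A measures W from the start of continuous enrolment to the first recorded fill. Patients flagged 2a but not 2b are therefore those whose first recorded fill follows too little enrolment. They have no earlier recorded fill, and some may be true initiators. The two places describe different added patients.

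**The case against.** The overlap is stated openly, and comparing an all-user analysis with a new-user restriction is an ordinary sensitivity comparison. The study objective concerns initiation, which the new-user analysis answers, so no primary estimate changes. The comparison leads only to exploratory work. All of that stands and limits the weight of the point.

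A reader might infer that the comparison was set up to expose prevalent-user bias and will fail to do so. The documents do not support this. The written rationale is more patients and confirmation of similar results; the bias-detecting purpose is only an inference from section 5. Nor is a missed trigger demonstrated: w and the prior-user hazard ratios are assumed, and each survivor-bias case in step 3 would still reach the borrowed 10% cut point. If new users are a small part of the combined cohort, the dilution is small.

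The mixing formula is also approximate, because section 5.6.1 plans a separate propensity score for prevalent use. The overlap destroys no information as such: a test using the variance of the nested difference (V_new − V_all) gives the same z as the disjoint test. The protocol specifies no such test, however, and names only a comparison of hazard ratios. A test could be left to an analysis plan, and section 5.6.2 refers to another protocol, not shown, for further details. The cohort definition and the comparison are nevertheless fixed here.

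A reader might also suppose that the Step 2 flags in Appendix A already isolate patients with prior insulin. They do not, as step 5 shows.

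**Conclusion.** The point holds in a limited form. All primary new users are in the prevalent-user analysis, so the planned comparison understates any difference between new users and patients with prior insulin. On the log scale the understatement is roughly the new users' share of the information. That share is not in the documents; between assumed values of 0.2 and 0.8, about 20% to 80% of the log difference is lost from view. The comparison can mask a discrepancy but is not shown to do so. Similar hazard ratios would be weak confirmation, while a clear difference would still be informative. The nesting follows from the text alone; the sizes rest on the assumed shares and ratios and on approximate log-scale mixing. This is a worthwhile, inexpensive improvement to a secondary comparison and does not affect the primary analysis.

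**What to change.** - Keep the combined prevalent-user cohort for its sample-size purpose.
- In section 5.6.2, base the substantial-difference comparison on two disjoint groups: new users, and patients excluded from the new-user analysis for insulin use in the 19 months before the first eligible prescription. Identify the second group by the exclusion rule in sections 5.1 and 5.2, not by the Step 2 flags in Appendix A.
- For each endpoint, report the ratio of the two hazard ratios (the treatment-by-prior-use interaction) with its confidence interval, by site and pooled, and make this the quantity that the trigger refers to.
- State whether patients flagged 2a but not 2b belong to the prevalent-user cohort, and align section 5.6.2 and Appendix A accordingly.

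The cost is one extra model per endpoint and some rewording. The prior-user estimate will have a wider interval than the combined one. As the breast figures in step 4 indicate, the contrast may be imprecise for individual cancers, and the interval would make that visible.
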